# 2.7 Rationale for Study Design

Study UV1-202 is a randomized, multicenter, open-label, active-controlled clinical study to document the efficacy and safety of adding UV1 vaccination to dual checkpoint blockade therapy with nivolumab plus ipilimumab.

## **Primary Endpoint**

Progression free survival is the primary endpoint of the study. In line with European Medicines Agency and FDA anticancer guidance, PFS is an acceptable primary endpoint in first-line metastatic disease, being reflective of clinical benefit. Progression free survival is considered an appropriate choice of endpoint especially when effective second-line therapies are available that would serve to confound subsequent OS outcome, as is the case in advanced malignant melanoma.

Median PFS with nivolumab plus ipilimumab in unresectable or metastatic melanoma has been reported to be 11.5 months (95% CI, 8.9 to 16.5) in the nivolumab plus ipilimumab group. Upon progression to more advanced melanoma, patients will likely receive subsequent effective anticancer treatment, including checkpoint monotherapy, chemotherapy, and targeted therapy, thus ruling out OS as a viable primary endpoint due to the diluting effect of these additional therapies.

Progression free survival is appropriate for evaluating the effect of a therapeutic cancer vaccine. The expected mode of action for a therapeutic peptide cancer vaccine is to induce proliferation of T cells recognizing epitopes within the vaccine peptides. The secondary effects of these T cells will depend on the individual patient's genetic, biochemical, and immunological status and may include increased frequency of tumor responses (increased ORR), prolonged DOR^34, and increased frequency and duration of SD. Progression free survival, unlike DOR or ORR, as primary endpoints is suited to capture all tentative efficacy attributes of the vaccine. The study is therefore formally powered for analysis of PFS. Overall survival will be analyzed as supportive evidence.

### **Treatment Arms**

UV1-202 is a randomized study with 2 arms, with the objective of documenting the add-on effect of UV1 vaccination to nivolumab and ipilimumab:

- Experimental arm: UV1 vaccination in combination with nivolumab and ipilimumab
- Control arm: nivolumab and ipilimumab

A 2-armed study will provide data on the efficacy and safety of UV1 vaccination as add-on to nivolumab and ipilimumab in patients with unresectable stage IIIB-D or unresectable metastatic melanoma which will suffice for hypothesis generation.

In addition to the 2-armed part of the study, 20 patients will be enrolled in a single arm UV1 cohort for collection of additional biological material to support the Extended Exploratory Cohort of the study. The single arm UV1 cohort is intended for exploratory purposes only (Appendix 7 Single Arm UV1 Cohort).

# 2.8 Benefit/Risk Assessment

The clinical studies completed to date (n=52) have demonstrated that UV1 vaccination is generally well tolerated, both as monotherapy and in combination with ipilimumab. There were no dose-limiting toxicities observed in the 2 dose-finding studies completed, and no apparent dose relationships in the rate of patients experiencing the most common related AEs (injection site related AEs). Anaphylactic reaction, anaphylactic shock, and hypersensitivity have been identified as AESIs for UV1 vaccination based on 5 events in 5 patients included in the completed studies.

Study UV1/hTERT-MM-103, investigating the use of UV1 in combination with the anti-PD-1 monoclonal antibody pembrolizumab, is currently ongoing for follow-up. 30 patients have been included and treated with UV1 and pembrolizumab. The combination of pembrolizumab and UV1 appears to be generally well tolerated. Nine serious adverse events (SAEs) for 7 patients (23.3%) in the study, the majority of which were considered unrelated to study treatment.

To reduce the risk for AESIs, a maximum of 8 UV1 vaccinations will be administered to the patients under the current protocol. Patients will remain at the study site for observation for at least 4 hours after each UV1 vaccination. Patients who develop serious allergic reactions during treatment with UV1 vaccinations will be discontinued from further UV1 vaccinations.

No information on the effects of UV1 vaccination on fertility and reproduction is available, and patients of childbearing potential must agree to use an adequate method of contraception prior, during, and after completion of treatment with UV1 vaccination.

Nivolumab and ipilimumab are approved for the patient population suggested in the current study, and the toxicity profile of the combination is well characterized. The toxicities reported in the studies investigating the use of UV1 vaccination in combination with single agent ipilimumab and single agent pembrolizumab in malignant melanoma have so far been modest. Since the use of UV1 vaccination combined with nivolumab and ipilimumab has not been investigated previously, the protocol specifies specific safety monitoring for the study.

The UV1 vaccine induces vaccine-specific CD4 T cell response in the majority of patients across indications. The immunogenicity of the peptides in UV1 is further supported by data from several long-term surviving patients with pancreatic cancer, lung cancer, and malignant melanoma treated with an earlier hTERT vaccine. The available clinical data on efficacy and reported AEs versus exposure from the completed and ongoing studies with UV1 indicates a favorable risk/benefit profile for UV1 vaccination. The underlying scientific rationale for

expected immunological synergy the use of UV1 vaccination in combination with nivolumab and ipilimumab justifies the present clinical study.

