Across the 3 completed Phase I/II studies, UV1 was administered with 75  $\mu$ g of the adjuvant sargramostim per vaccination for up to 18 vaccinations. Localized dermal injection site reactions indicative of an inflammatory reaction to sargramostim and hence recruitment of dendritic cells to the injection site were seen in 63% of patients and 78% developed a vaccine-specific immune response. This supports the use of 75  $\mu$ g sargramostim per UV1 vaccination for the further clinical development of UV1.

To reduce the risk for serious allergic reactions to UV1 and/or sargramostim, the number of vaccinations with UV1 and sargramostim have been limited to 8 vaccinations over a period of 73 days in the current protocol. The serious allergic reactions observed in 5 patients (10%)

occurred within 3 to 30 minutes after administration of the 9th or more vaccinations (>20 weeks of exposure). The immune response data from the completed study investigating the use of UV1 with ipilimumab in patients with malignant melanoma support that 8 UV1 doses sufficed to generate a vaccine-specific immune response. The patients in that study received an average of 5.5 UV1 vaccinations (range 3 to 9), and 91% of the evaluable patients had immune response within 12 weeks after first vaccination.

In the current study, a dose of 75  $\mu$ g sargramostim will be injected intradermally 10 to 15 minutes prior to intradermal injection of UV1 at the same site.

The 75  $\mu$ g sargramostim dose is the same dose that has been used in the 3 completed Phase I/II studies with UV1 and in 10 out of 30 patients in the UV1/hTERT-MM-103 study.

Patients in the experimental arm will receive 8 UV1 vaccinations over 4 cycles of nivolumab and ipilimumab. UV1 vaccination will be administered alone on Days 1, 3-7 (2 UV1 vaccinations within Day 3 to Day 7, consecutive dosing days not allowed) and 26, and in combination with nivolumab and ipilimumab on Days 10, 31, 52 and 73. The administration regimen for UV1 vaccination during Days 1-10 is optimized for synergy with ipilimumab leading to effective priming and expansion of naïve hTERT specific T cells in the local lymph node draining the vaccine injection site. At Days 26 and 73, the UV1 vaccinations are optimized for re-activation and effector activity of the vaccine induced T cells in the tumor micro-environment in synergy with nivolumab and ipilimumab.

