#### Figure 3 McBurney's Point

Administration of UV1 should be done **10 to 15 minutes** *after* the administration of sargramostim. The UV1 is to be administrated at the exact same site as the sargramostim.

Allergic reactions may occur after sargramostim and UV1 injections. Therefore, patients should remain at the site for observation for at least 4 hours after each UV1 injection.

Nivolumab and ipilimumab are administered intravenously according to the label and administration is to be started at least 1 hour after the injection of UV1.

Patients in the experimental arm will receive 8 UV1 vaccinations over 4 cycles of nivolumab and ipilimumab. The UV1 vaccination will be administered alone on Days 1, 3 to 7 (2 UV1 vaccinations), and 26, and in combination with nivolumab and ipilimumab on Days 10, 31, 52, and 73.

Patients in the control arm will receive 4 cycles of nivolumab and ipilimumab, on Days 1, 22, 43, and 64.

The administration of sargramostim, UV1, nivolumab, and ipilimumab must be recorded in the patients' medical files and the appropriate section of the electronic Case Report Form (eCRF). The reason for dose interruption, reduction, or omission will also be recorded in the medical files of patient and later in the eCRF. This information will be used to assess compliance with treatment.

Following the induction therapy, patients in both treatment arms will start maintenance therapy and receive nivolumab at a dose of 480 mg Q4W according to the label. It is not allowed to use any other dose of maintenance therapy (eg, 240 mg Q2W). Nivolumab is the standard of care and should be monitored according to the institutional practice (including routine blood sampling).

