## 8.2 Safety Plan and Assessments

The administration of study treatment will be performed in a setting with emergency medical facilities and staff who are trained to monitor for and respond to medical emergencies. Eligibility criteria were selected to guard the safety of patients in this study. During the study, patients will be closely monitored for the development of any AEs, including signs or symptoms of

autoimmune conditions. Patients receiving UV1 injections will be observed in study site for 4 hours following each treatment with UV1 and sargramostim.

Planned timepoints for all safety assessments are provided in the schedule of activities. Adverse events will be reported throughout the study as described in Section 8.3. Any clinically significant abnormalities persisting at the PFS cut-off date reached will be followed by the Investigator until resolution or until a stable clinical status is reached but will not be recorded in the eCRF; however, clinically significant abnormalities should be noted in the patient's medical file.

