# 8.3.1.5 Definition of Adverse Event of Special Interest

Adverse events of special interest are events of scientific and medical interest specific to the further understanding of the safety of UV1 vaccination. An AESI may be serious or non-serious. For all AESIs, the Investigator should provide a description of the event, including but not limited to time of onset, treatment given, and outcome. Events falling under the AESI definition is an AESI regardless of the investigator's assessment of relatedness to a study drug, and regardless of which treatment arm the patient is randomized to.

Adverse events of special interest include any of the following events occurring on the same day of sargramostim, UV1, nivolumab or ipilimumab administration:

- Anaphylactic shock
- Anaphylactic reaction
- Hypersensitivity (allergic reactions except local injection site reactions).

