## 8.3.3 Adverse Event Reporting and Follow-up

# 8.3.3.1 Reporting

Adverse events will be reported by the patient (or, when appropriate, by a caregiver, surrogate, or the patient's legally authorized representative). Care will be taken not to introduce bias when detecting AEs. Open-ended and non-leading verbal questioning of the patient is the preferred method to inquire about AE occurrence (for example, "Have you experienced any new or changed symptoms since we last asked/since your last visit?").

From signing of the ICF until the first dose of induction therapy, only AEs/SAEs caused by study-specific procedures should be reported. All non-serious AEs should be reported from the first dose of induction therapy until 30 days after the last dose of induction therapy, or until new anticancer treatment is initiated (whichever comes first).

All SAEs should be reported from the first dose of induction therapy until 70 PFS events are reached, until 18 months post last patient randomized or until new anticancer treatment is initiated (whichever comes first).

The time periods for reporting of AEs and SAEs are outlined in Figure 4.

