#### Sample Collection and Assessments

The sample collection and assessments in the Extended Exploratory Cohort will be done in addition to those requested elsewhere per protocol. In the experimental arm these will be done during the Screening period, and at Days 1, 31, and 52. In the control arm these will be done during the Screening period, and at Days 1 and 43. In both treatment arms sample collection and assessment will also be done at the safety follow-up visit and 18 weeks post last dose of induction therapy. Sample type and assessments are described in Table 9 and Table 10 below.

Visit	Assessment	Volume of tissue collected
Screening	Fecal sample	Dedicated sample card
	Tumor biopsy (FFPE biopsy)	At the pathologist's decision (one biopsy)
	Tumor biopsy (Snap-frozen biopsy)	At the pathologist's decision (two snap-frozen)
Day 1	Whole blood for DNA	3 mL blood
	SNP sample	3 mL blood
	Whole blood for PBMC	80 mL blood
	DTH a	Not applicable
Day 31	Whole blood for PBMC	80 mL blood
	DTH a	Not applicable
Day 52	DTH a	Not applicable
Safety follow-up	Whole blood for PBMC	80 mL blood
	Tumor biopsy (FFPE biopsy)	At the pathologist's decision (one biopsy)
	Tumor biopsy (Snap-frozen biopsy)	At the pathologist's decision (two snap-frozen)
	DTH a	Not applicable
18 weeks post last dose	Whole blood for PBMC	80 mL blood
of induction therapy	DTH a	Not applicable
(2 nd response follow-up		
visit)		
Total blood volume		326 mL blood / patient

#### **Extended Exploratory Cohort Assessments – Experimental Arm** Table 9

Abbreviations: DNA = deoxyribonucleic acid; DTH = delayed-type hypersensitivity; FFPE = formalin fixed, paraffin embedded; PBMC = peripheral blood mononuclear cell; SNP = single nucleotide polymorphisms.

a UV1 without sargramostim intradermally in the skin of the anterior forearm. Patient will measure and record the skin reaction 48±4 hours after the injection.

Tuble 10 Entended Emploratory Condition Social Entended Emploratory	Table 10	Extended Explorator	y Cohort Assessments –	Control Arm
--	----------	---------------------	------------------------	-------------

Visit	Assessment	Volume of tissue collected
Screening	Fecal sample	Dedicated sample card
	Tumor biopsy (FFPE biopsy)	At the pathologist's decision (one biopsy)
	Tumor biopsy (Snap-frozen biopsy)	At the pathologist's decision (two snap-frozen)
Day 1	Whole blood for DNA	3 mL blood
	SNP sample	3 mL blood

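### DTH testing adds up to five UV1 injections that the benefit/risk text does not mention, and non-serious AESIs after the last (and usually the fourth) fall outside AE reporting

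*Combined protocol and SAP*

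**What the plan says.** **The cap.** Section 2.8 gives it as "a maximum of 8 UV1 vaccinations will be administered to the patients under the current protocol", and section 2.6 as "the number of vaccinations with UV1 and sargramostim have been limited to 8 vaccinations over a period of 73 days". Section 2.6 gives the reason: the five serious allergic reactions in earlier studies came at the 9th or a later vaccination, after more than 20 weeks of exposure. Section 2.3 defines a UV1 vaccination as sargramostim and UV1 together.

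**DTH testing.** Experimental-arm patients in the Extended Exploratory Cohort are tested at five timepoints: Days 1, 31 and 52, the safety follow-up visit, and 18 weeks after the last induction dose (Appendix 2, Table 9). Each test is "UV1 without sargramostim intradermally in the skin of the anterior forearm", using 20 µL of the reconstituted solution (section 6.1.2.1). Appendix 7 applies the same procedures to all 20 single arm patients.

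**AESIs and reporting.** Section 8.3.1.5 defines AESIs as "any of the following events occurring on the same day of sargramostim, UV1, nivolumab or ipilimumab administration" and allows them to be serious or non-serious. Section 8.3.3.1 states: "All non-serious AEs should be reported from the first dose of induction therapy until 30 days after the last dose of induction therapy". The window closes earlier if the patient starts another anticancer treatment. SAEs run to the PFS cut-off (to end of study in the single arm cohort), also ending at new anticancer treatment. No separate AESI window is given, and the 24-hour list in section 8.3.4 names only SAEs and pregnancies.

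**Observation.** Section 6.1.5 says "patients should remain at the site for observation for at least 4 hours after each UV1 injection". Section 8.2 says "4 hours following each treatment with UV1 and sargramostim". Section 2.8 ties the period to each UV1 vaccination.

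**The concern.** Allergic reaction is the safety signal the protocol singles out for UV1, and the stated mitigation is to limit repeated exposure. The DTH subset receives more UV1 injections, and over a longer period, than any other patients in the study. The benefit/risk text does not mention that exposure.

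The AESI definition covers a DTH injection, because it is a UV1 administration. The reporting window was built around induction and closes before the last test. If a non-serious hypersensitivity reaction follows that test, the protocol gives the site no route to report it. An absence of events at the highest cumulative exposure could then mean either that none occurred or that none were collected.

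The observation wordings raise a smaller matter. At a visit with a DTH injection and no vaccination, section 6.1.5 applies as written, while sections 2.8 and 8.2 speak only of vaccination or of UV1 with sargramostim.

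**Working it through.** **Step 1. Reproduce the stated cap.** Vaccination days (section 4.1): Day 1 (1), two within Days 3-7 (2), Day 26 (1), and Days 10, 31, 52 and 73 (4). 1 + 2 + 1 + 4 = 8, the last on Day 73. This matches the 8 vaccinations over 73 days in section 2.6.

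**Step 2. Add the DTH injections.** 8 + 5 = 13 intradermal UV1 injections. On shared days the test precedes the vaccination (section 6.1.2.1).

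| Visit | UV1 given | Running count |
|---|---|---|
| Day 1 | DTH, vaccination | 2 |
| Days 3-7 | two vaccinations | 4 |
| Day 10 | vaccination | 5 |
| Day 26 | vaccination | 6 |
| Day 31 | DTH, vaccination | 8 |
| Day 52 | DTH, vaccination | 10 |
| Day 73 | vaccination | 11 |
| Safety follow-up | DTH only | 12 |
| 18 weeks after last induction dose | DTH only | 13 |

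**Step 3. Amount of UV1.** The concentration is 3.0 mg/mL (section 6.1.2).
- Per test: 0.020 mL × 3.0 mg/mL = 0.060 mg = 60 µg
- Five tests: 5 × 60 = 300 µg
- Eight vaccinations: 8 × 300 = 2,400 µg
- Ratio: 300 / 2,400 = 12.5%, or one vaccination's worth of UV1

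**Step 4. Dates, with the last induction dose on Day 73.**
- End of non-serious AE reporting: 73 + 30 = Day 103
- Safety follow-up visit, 30 to 37 days after the last dose (section 7.3.1): Days 103 to 110
- 18-week test: 73 + 18 × 7 = 73 + 126 = Day 199; with the ±1 week window, Days 192 to 206
- Time from Day 1: (199 − 1) / 7 = 28.3 weeks

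**Step 5. Compare each DTH-only visit with the window.**
- 18-week test: 199 − 103 = 96 days past the limit. The earliest permitted date is still 192 − 103 = 89 days past it.
- Safety follow-up test: inside on day 30 after the last dose, outside on days 31 to 37. That is 7 of the 8 permitted days.

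The adverse event row in Table 5 is marked at response follow-up, but footnote g applies the same 30-day limit to non-serious events, so the table does not close the gap.

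**Step 6. Compare with the earlier exposure pattern.** Twenty weeks from Day 1 is 1 + 140 = Day 141. The 9th UV1 injection by count is the Day 52 test, about week 7. The safety follow-up test (Days 103-110) is about week 15-16. Only the Day 199 test is both beyond the 8th injection and beyond 20 weeks.

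**The case against.** Several stronger readings are tempting, and the documents do not support them.

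- **The cap is broken, with 13 given instead of 8.** The cap counts vaccinations, defined as UV1 plus sargramostim. A DTH test has no sargramostim and one fifth of the UV1 dose. The two counts are in different units, so there is no literal breach.
- **The earlier risk threshold is passed on Day 52.** Earlier reactions followed nine or more doses of UV1 with sargramostim and more than 20 weeks of exposure. Only the Day 199 test passes both markers by injection count, and it is 60 µg without adjuvant.
- **Events after both late tests are always lost.** A reaction at a safety follow-up visit held on day 30 is still inside the window.
- **Serious reactions go unreported.** They remain reportable as SAEs at both visits unless new anticancer treatment has started. The five events that led to the AESI definition were all serious, so that kind of event is still captured.
- **All patients are affected, or all 40 reach 13 injections.** No one outside these cohorts has DTH tests. Testing stops if UV1 is discontinued (section 7.2.1) or induction ends early (Appendix 2), and patients with confirmed progression move to survival follow-up. About 20 plus 20 is a ceiling.
- **A planned AESI rate will be biased.** Section 9.4.3 specifies no AESI rate or table. The single arm patients are not randomized, so they are outside the safety population.
- **The observation texts contradict each other.** Section 6.1.5 covers every UV1 injection; sections 2.8 and 8.2 are silent on DTH-only visits and do not exempt them. On Days 1, 31 and 52 a vaccination is given, so every wording applies.

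One caution bears on the remedy. Collecting extra AESIs on DTH-only days and pooling them would create unequal ascertainment, because controls have no such visits.

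What stands is the unmentioned exposure and a defined AESI with no reporting route when it is non-serious and late.

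**Conclusion.** The point holds in a limited form. Up to about 40 patients receive as many as five further UV1 injections (+300 µg, +12.5%), out to about Day 199, that the dose rationale and benefit/risk sections do not mention. Non-serious AESIs after the 18-week test always fall outside reporting, and those after the safety follow-up test do so unless the visit is on day 30. The primary and secondary efficacy analyses are untouched.

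The conclusion assumes that a DTH injection is not a dose of induction therapy. The documents support this: the experimental-arm induction period ends on Day 73, and the safety follow-up visit, which itself includes a DTH injection, is timed from the last induction dose. It also assumes nominal timing, with the last dose on Day 73. The ±2 day dosing window moves the calendar days, but not the 30-day limit relative to the last dose. How many patients reach the late tests is not stated, so the number of events at risk of being missed cannot be estimated.

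This is worth correcting because the loss concerns the protocol's own UV1 safety signal and the visits already exist.

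**What to change.** 1. In section 8.3.3.1 and Table 5 footnote g, extend reporting to all AESIs, serious or not, that occur on the day of any UV1 injection, including DTH tests.
2. Count DTH injections in the summary of UV1 exposure.
3. Tabulate AESIs from DTH-only visits separately from the between-arm AE comparison.
4. State the DTH exposure (number, amount, timing) in sections 2.6 and 2.8 beside the 8-vaccination cap.
5. Reconcile the observation wordings in sections 2.8, 6.1.5 and 8.2 for DTH-only visits, so that sites have one instruction. Which rule applies is for the sponsor to decide.

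**Cost.** Protocol wording, one extra AE-collection day at two existing visits for at most about 40 patients, and one additional table. No visit, procedure or endpoint changes. The planned timelines put the last single arm patient in H1 2023, so many of these tests may already have been done. For those, items 2 to 4 remain feasible, and the report should state that non-serious AESIs were not collected after the late tests.
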